### **Carotid Artery Ultrasound**

There is no risk or discomfort associated with this procedure.

### **Metformin Intervention**

Adverse effects of metformin include nausea, anorexia and diarrhea, and reduction in blood sugar due to improved insulin sensitivity. The adverse GI effects could potentially interfere with patient compliance. These effects have been shown to be reduced when the dose is titrated up slowly, given with food, and when blood sugars are followed closely as described in the Study Design section. Metformin has been found to rarely cause lactic acidosis (about 0.03 cases per 1,000 person years), and then only when used in persons with renal or hepatic insufficiency or during episodes of hypoxia or circulatory failure. This risk is minimized by stopping the medication with vomiting, diarrhea, before IV contrast or alcohol ingestion, and by the screening safety labs. A very rare risk of anemia is possible, but minimized by a screening and post-intervention check for anemia. We have already obtained an FDA exemption for use of metformin in this study. Metformin is often used to help women get pregnant and continued in the first trimester of pregnancy. However, to maximize safety, pregnancy is an exclusion criterion in the study.

### **Violation of Privacy and Loss of Confidentiality**

These are both risks to which research participants are exposed. The possibility of these risks increases when protected health information is collected. Every effort will be made to decrease this risk by limiting access to protected health information, storing this information in a password protected database, and identifying subjects only by a unique identifier that is kept in a separate location in a locked container, traceable only by study personnel. All of the tests involve the risk of identifying asymptomatic abnormalities. The study may include risks that are unknown at this time.

## **10. Protection Against Risks**

Study diet: Subjects will be asked to monitor blood sugars at least four times a day for the 3 days prior and the 24 hours after the study. Subjects will be called to check on blood sugars. Insulin doses will be adjusted as indicated.

Glucose levels will be monitored closely during both the clamp study and the overnight insulin infusion to avoid hypoglycemia in diabetic subjects. Women will have a urine pregnancy test performed in order to ensure that neither the DEXA nor the clamp study is performed on any woman who is currently pregnant.

Proper sterile technique will be used with blood draws and IV placement to decrease the infection risk. EMLA cream will be used if subject desires to minimize pain of IV. Frequent, rapid blood glucose measurements will be monitored during the euglycemic clamp to ensure safety.

To minimize the risk of any complications with the clamp, during the entire clamp procedure, a pediatric CTRC nurse will remain at the bedside, and a Pediatric Endocrinologist (study Physician) or study Nurse Practitioner or study Physician Assistant will also remain at the bedside. The IV site will be continuously monitored.

To minimize the risk of hypoglycemia in diabetic subjects during the VO2max test, blood glucose levels will be monitored before and after the test. Snacks and juice will also be available for subjects during the test. A light meal will also be provided to subjects follow the exercise test. To minimize GI side effects of metformin or hypoglycemia, the dose is titrated up slowly, given with food, and blood sugars are followed closely as described in the Study Design section. In addition, in the preliminary studies presented the effect of metformin on HbA1c was small, and the meta-analysis cited found no significant effect on HbA1c, therefore major changes in blood sugars are not expected. Other adverse effects of metformin include lactic acidosis. This side effect is extremely rare and is associated with dehydration. The risk of lactic acidosis will be decreased by having the subject stop their metformin temporarily if they are going to have surgery, IV contrast, alcohol ingestion or a significant illness associated with vomiting. Anemia is avoided by a screening and post-intervention Hb, and by blood volumes within recommended guidelines.

Emergency Response Plan: EKG, echocardiogram and blood pressure measures are performed prior to exercise testing to screen for any heart problems making exercise contraindicated. A physician or trained proctor will be present during the test. The CTRC performs graded exercise testing on a regular basis and is equipped with an oxygen supply and defibrillator. In the event that a patient goes into cardiac arrest during the procedure, the research team will call 911.

Blood Volume: We will use a minimum weight cutoff of 26 kg to remain below the most conservative pediatric CTRC blood drawing guidelines. In addition, we pre-screen subjects with a hemoglobin and hematocrit at their baseline visit, and exclude subjects with anemia. This screening also helps to increase the safety of the blood draw. In addition, the blood planned to be frozen and held could also be omitted if needed to reduce blood volume for a particular subject. Finally, our CTRC has a system to track other studies subjects might enroll in, and we ask during our consent process if the subject has been involved in any other studies in the past 6 weeks to avoid excessive blood drawing.

Pregnancy: Pregnancy is an exclusion criterion in the study and is tested for prior to each DEXA and insulin clamp.

Every effort will be made to decrease the risk of loss of confidentiality by limiting access to protected health information, storing this information in a password protected database, and de-identifying study specimens.

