### **Visit 1 (Screen Visit)**

Pediatric CTRC Outpatient unit or Endocrinology clinic: Participants will begin with a screening and randomization visit. During this visit, patients will review and complete consent documents, have demographics and medical history confirmed, assess allergies and inclusion/exclusion criteria, have blood samples drawn, and have anthropometrics completed. HbA1c, Cr, ALT, AST and Hb samples will be drawn at the beginning of the visit after consent. At the completion of the screening visit, the subject will be given an accelerometer to be worn for the following seven days to measure level of habitual physical activity.

In addition, subjects will be educated on checking blood glucose frequently (minimum of 4 times a day), and on parameters for contacting study staff.

If subjects meet entry criteria, they will be invited to come in for the baseline assessments as soon as feasible.

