#### **Visit 5 (Pill Count Verification)**

Subject will come back in 45 days (+/- 5 days) from Visit 4 with all opened and unopened pill bottles to assess compliance, GI side effects, adverse events, changes in concomitant medications and medical history, height, weight, BP, WC, HC, HbA1c, AST, ALT, serum Cr, Hb and blood sugars. An additional 8 weeks of metformin or placebo will be dispensed. The final assessment visits, if not already scheduled, will be finalized. The subject will be given an accelerometer to be worn again for the following seven days to measure level of habitual physical activity.

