#### **Visit 7 (Repeat Exercise Visit)**

This visit will follow the same procedures as the Baseline Exercise Visit (Visit 3). Please refer to the description above for procedure details, except that study medication will be withheld the AM of fasting.

**Visit 8 (Repeat Clamp Visit)** This visit will follow the same procedures as the Baseline Clamp Visit (Visit 4). Please refer to the description above for procedure details, except that study medication will be withheld the AM of fasting. Study medication will be discontinued after this visit. The subject will return all opened and unopened pill bottles during this visit. During this visit, subjects will also be given recommendations and education on increasing their amount of exercise due to their identification of being sedentary.

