### Fasting Blood Draw

Just prior to starting the insulin clamp, blood will be drawn for HbA1c, C-peptide, lipid panel, glucose, glycerol, background enrichment of 6,6-H2 glucose and H5glycerol, insulin, free fatty acids, c-reactive protein, Creatinine, , AST, ALT, DHEAS, Testosterone, Estradiol, Progesterone, sex hormone binding globulin, high molecular weight adiponectin, lipid subfractions (via FPLC in laboratory of [name]), NT-pro-BNP and apo-B and apo-C3, I-CAM, V-CAM and T-BARs (run in the laboratory of [name]).

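### The risk sections rely on a post-intervention hemoglobin check, but the protocol schedules hemoglobin only at screening and at the mid-treatment Visit 5

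*Combined protocol and SAP*

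**What the plan says.** The safeguard is stated twice. Under Metformin Intervention in section V.9: "A very rare risk of anemia is possible, but minimized by a screening and post-intervention check for anemia". In section V.10, Protection Against Risks: "Anemia is avoided by a screening and post-intervention Hb, and by blood volumes within recommended guidelines". The first statement concerns anemia from metformin only. The second speaks of anemia in general and lists limits on blood volume as a separate protection.

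The visit descriptions place hemoglobin at two points.

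- Visit 1 (Screen Visit): "HbA1c, Cr, ALT, AST and Hb samples will be drawn at the beginning of the visit after consent".
- Visit 5 (Pill Count Verification): the laboratory list reads "HbA1c, AST, ALT, serum Cr, Hb and blood sugars", and the timing is "Subject will come back in 45 days (+/- 5 days) from Visit 4". Eight further weeks of study medication are handed out at this visit.

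The Hemoglobin row of Table 2 is marked at the same two visits. The Blood Samples text in V.9 mentions hemoglobin only for the baseline and interim visits.

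Visit 8 repeats the Visit 4 procedures, and its text adds: "Study medication will be discontinued after this visit". The clamp-day panel under Fasting Blood Draw begins "Just prior to starting the insulin clamp, blood will be drawn for HbA1c, C-peptide, lipid panel, glucose, glycerol" and goes on to creatinine, AST and ALT, among others. Hemoglobin is not in it.

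**The concern.** A post-intervention check on a drug course would ordinarily be read as one made when the course has ended. The protocol has an end-of-treatment visit with a large blood sample, and hemoglobin is not on its list. A site that follows the schedule exactly will therefore never perform the check that the two risk passages rely on.

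What is at stake is the accuracy of a safety statement. Anyone who judges the trial's risk from V.9 and V.10, such as the institutional review board or the Safety Officer, would believe that each participant who finishes treatment has a hemoglobin value from that time. Under the schedule as written, the latest planned value comes from about the middle of treatment. The participants are aged 12 to 21 and many are minors, so the stated protections should match what is done.

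**Working it through.** No power or sample-size figure is involved. The check compares every place where hemoglobin could be scheduled, followed by simple date arithmetic.

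**Step 1. Where hemoglobin appears**

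| Time point | Source | Hemoglobin? |
|---|---|---|
| Visit 1, screening | Visit 1 text; Screening Blood Draw; Table 2 | Yes |
| Visits 2, 3 and 4, baseline | Visit texts; Fasting Blood Draw for the clamp | Not listed |
| Visit 5, day 45 +/- 5 | Visit 5 text; Table 2 | Yes |
| Visits 6, 7 and 8 | Stated to repeat Visits 2, 3 and 4 | Not listed |
| Phone Interview 3, one week after Visit 8 | Phone Interview 3 text | No blood taken |

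Table 2 is not complete on its own. It marks creatinine, AST and ALT at Visits 1 and 5 only, although Fasting Blood Draw also takes them at the clamp, and it marks the accelerometer only at Visit 1, although Visit 5 repeats it. An unmarked cell is therefore weak evidence. Here the visit texts, the clamp panel and the Blood Samples text all agree with the table.

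**Step 2. Is Visit 5 post-intervention?** Drug starts at dinner after the Visit 4 clamp, so Visit 5 is at about day 45 of treatment. The protocol calls it interim in the Study Visits narrative, in Duration of Participation and in Blood Samples. Phone Interview 2 says that study drug continues until Visit 8 is completed. Visit 5 is therefore a mid-treatment visit by the protocol's own account.

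**Step 3. Treatment time after the last scheduled value**

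Formula: days without a later value = course length - day of Visit 5.

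The protocol gives the course as 3 months and does not fix Visit 8 to a day. The lengths used are assumptions: 90 days as the central value, 84 days (12 x 7) as a short course, and 98 days as a long one, which is all the medication dispensed ((6 + 8) weeks x 7).

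| Course (days) | Visit 5 at day 40 | Visit 5 at day 45 | Visit 5 at day 50 |
|---|---|---|---|
| 84 | 44 | 39 | 34 |
| 90 | 50 | 45 | 40 |
| 98 | 58 | 53 | 48 |

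As a share of the course, the last hemoglobin falls at 45/90 = 50% in the central case. The extremes are 40/98 = 41% and 50/84 = 60%.

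**The case against.** The best defense is that the check exists and is only loosely named. Visit 5 sits under the treatment-assessment columns of Table 2. It comes after six weeks or so on drug and after the first large clamp draw, and at a time when withdrawal is still possible. If post-intervention was meant as after the start of the intervention, only the wording is at fault. This has force: the Visit 5 value is a real protection, and correcting the wording is a legitimate way to reconcile the passages. It does not remove the contradiction, because the protocol labels Visit 5 interim and gives drug for weeks afterwards.

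The protocol also calls the risk very rare, excludes participants with hemoglobin below 9 and withdraws those who fall below 9. It asks about adverse events at visits and phone interviews, including the call after Visit 8. A reader might infer that anemia arising after Visit 5 would go unnoticed. The documents support only that no scheduled laboratory test would find it.

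Other stronger readings are tempting and do not stand.

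- *That the plan promises, and fails to make, a check on the second clamp draw of 130.8 ml.* The V.9 metformin text does not mention blood drawing. For blood drawing, Blood Samples and the Blood Volume paragraph rely on screening, a weight cutoff and volume limits.
- *That a Visit 8 hemoglobin would protect participants at the second clamp or serve the withdrawal limit.* A sample taken just before the clamp cannot show a fall caused by that draw, and its result need not be known before the clamp begins. Study drug stops at that visit anyway.
- *That the trial loses a needed comparison of hemoglobin by arm.* Hemoglobin is not among the primary or secondary outcomes or in the Data Analysis Plan.
- *That no participant has a late value.* Under Subject Compensation, Visits 4 and 8 of co-enrolled participants are performed by another study, whose laboratory list is not in these documents.

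**Conclusion.** The contradiction holds. Two risk passages name a post-intervention hemoglobin check, and this protocol schedules no hemoglobin at or after the end of treatment. The last scheduled value leaves 40 to 50 days of a 90-day course without a later one, or 34 to 58 days if the course runs 84 to 98 days. These figures rest on the assumed course lengths and on Visit 5 being held within its window. They describe scheduled tests under this protocol only.

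It is a minor to moderate internal inconsistency in a safety safeguard. It does not touch the efficacy analysis, and it does not show that participants are exposed to a material anemia risk. The documents give no figure for that risk beyond calling it very rare.

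**What to change.** Reconcile the anemia statements in V.9 (Metformin Intervention) and V.10 with Table 2, the Visit 5 and Visit 8 texts, Fasting Blood Draw and Blood Samples. Either route removes the contradiction, and the choice belongs to the sponsor.

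1. Add hemoglobin to the Visit 8 column of Table 2 and to the pre-clamp fasting sample at that visit, so that the stated check exists. This needs a small amendment, one more analyte on a sample already drawn, and about 1 ml of blood. That volume is an estimate: the protocol gives none for hemoglobin alone, but allows 5 ml or less for the whole screening or interim panel. The amendment should describe the result as an end-of-treatment value and claim no more for it.
2. Leave the schedule as it is and restate the safeguard in V.9 and V.10 as a screening and mid-treatment check. This costs a text change only.

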## 9. Potential Risks to Subjects

### Blood Samples

The collection of blood samples may result in temporary discomfort, bruising, bleeding, and on rare occasions, infection.

Nationally, the NIH Clinical Center has a guideline of 9ml/kg in 6-8 weeks for pediatric studies. Certain studies at our institution do draws over 7ml/kg in 6 weeks, or up to 7 ml/kg in a single draw, but include iron supplementation. Otherwise, the routine guidelines in our Pediatric CTRC are 3ml/kg for a single draw and no more than 7ml/kg over an 8 week period. Our baseline and interim visits will include 5 ml or less of blood (1 tsp) (HbA1c, Hb, Cr, AST, ALT). The insulin clamp visit now includes 130.8 ml of blood, which includes 10.8 ml to check blood sugar every 5 minutes by glucometer for the 4.5 hour clamp.). Thus, our insulin clamp visit is within the more conservative pediatric CTRC guidelines of 3ml/kg for a single draw for pediatric studies for subjects 26 kg or greater. This is unlikely to exclude many subjects, as we have already excluded pre-pubertal subjects, and subjects with BMI<5% (due to potential undiagnosed illness), those groups likely to be the lightest in weight. Therefore, we will limit recruitment to subjects 26 kg or greater if all studies are performed. In addition, by study design, subjects <5% for weight are excluded as are subjects with anemia, screened by our baseline Hb, further increasing the safety of the study regarding blood draws. The two clamp visits are separated by 3 months, and therefore the significant blood draws are spaced enough apart to also fall within guidelines.

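### The consent question about other studies looks back 6 weeks, the cumulative blood-draw guideline counts 8, and no repeat of the question before either clamp is described

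*Combined protocol and SAP*

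**What the plan says.** Section 9 (Potential Risks to Subjects, Blood Samples) of the combined protocol and SAP cites several limits. As national context, "the NIH Clinical Center has a guideline of 9ml/kg in 6-8 weeks for pediatric studies". It adds that some studies at the institution go above 7 ml/kg in 6 weeks, with iron supplements. The routine limits of the pediatric research unit (CTRC) are 3 ml/kg for one draw and, cumulatively, "no more than 7ml/kg over an 8 week period".

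"The insulin clamp visit now includes 130.8 ml of blood", and this is described as "within the more conservative pediatric CTRC guidelines of 3ml/kg for a single draw for pediatric studies for subjects 26 kg or greater". The section then relies on spacing: "The two clamp visits are separated by 3 months", so the large draws are said to meet the guidelines as well.

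Section 10 (Protection Against Risks, Blood Volume) names two safeguards against blood drawn in other research, in one sentence. First, "our CTRC has a system to track other studies subjects might enroll in". Second, staff ask at consent "if the subject has been involved in any other studies in the past 6 weeks to avoid excessive blood drawing". The 6 weeks belong to the question; the tracking system has no stated period.

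Consent takes place at Visit 1. The items listed for Visits 4, 5 and 8 and for Phone Interviews 1 and 2 include adherence, side effects, medication and history changes, and glucose. Participation in other studies is not among them. The exclusion criteria do not bar a participant from joining another study later.

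**The concern.** A question meant to protect a cumulative limit should look back over the period that the limit counts, and be asked close enough to the large draw for that period to be covered. Here the look-back is two weeks shorter than the guideline period, and the question belongs to consent, whereas the two large draws come later. The second comes about three months after the first.

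At stake is whether the protocol can show that a participant who gives blood elsewhere stays within the cumulative guideline at each clamp. Section 10 also relies on guideline-compliant blood volumes as one of its protections against anemia.

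**Working it through.** Inputs from the documents: look-back 6 weeks = 42 days; guideline period 8 weeks = 56 days; cumulative guideline 7 ml/kg; clamp 130.8 ml; baseline and interim visits at most 5 ml each; minimum weight 26 kg; Visit 5 at 45 ± 5 days after Visit 4.

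Assumptions: three months between clamps is taken as 84 to 91 days. The time T from consent to the first clamp is not fixed in the protocol and is varied from 0 to 56 days.

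**1. The plan's own spacing statement.** 84 to 91 days exceeds 56, so the two clamps never share an 8-week period. Visit 5 falls between 84 − 50 = 34 and 91 − 40 = 51 days before Visit 8, inside the period. This trial's own draws in the 8 weeks to Visit 8 are therefore at most 5 + 130.8 = 135.8 ml. At 26 kg that is 135.8 / 26 = 5.2 ml/kg, against a guideline volume of 7 × 26 = 182 ml. The trial alone meets the cumulative guideline, with 182 − 135.8 = 46.2 ml left for any other study.

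**2. Days before the first clamp that the question covers.** It covers days T + 1 to T + 42 before the clamp; the guideline counts days 1 to 56.

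| T (days) | Covered | Uncovered of 56 |
|---|---|---|
| 0 to 14 | 42 | 14 |
| 21 | 35 | 21 |
| 28 | 28 | 28 |
| 42 | 14 | 42 |
| 56 | 0 | 56 |

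The minimum gap is 56 − 42 = 14 days. Beyond T = 14 the gap equals T.

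**3. Days before the second clamp.** Consent lies at least T + 84 days earlier, so even the consent date is outside the 56 days. Coverage is 0 of 56 for every T and interval tried. Lengthening the consent look-back to 56 days still gives 0 of 56, because a look-back from consent only reaches further into the past.

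**4. Illustration of size.** The documents give no volume for other studies, so x = 50, 78 and 130.8 ml are assumptions. The weight below which 7 ml/kg is exceeded is (135.8 + x) / 7:

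- x = 50: 185.8 / 7 = 26.5 kg
- x = 78: 213.8 / 7 = 30.5 kg
- x = 130.8: 266.6 / 7 = 38.1 kg

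**5. A related figure that does not reproduce.** 130.8 / 26 = 5.03 ml/kg, not 3 ml/kg; at 3 ml/kg the clamp volume corresponds to 130.8 / 3 = 43.6 kg. This conflict is separate, but it bears on step 4: at 43.6 kg the largest assumed case is 266.6 / 43.6 = 6.1 ml/kg, below 7.

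**The case against.** The strongest objection is that the question is only half of the safeguard. The tracking system appears first in the same sentence and is not tied to consent or to 6 weeks. A reader might infer from the day counts that nothing checks outside blood draws before the second clamp. The documents do not support that: the system's coverage is unstated, not zero. Equally, they do not say what period it covers, whether it sees studies outside the unit, whether it records volumes, or when it is consulted. They therefore do not show that it fills the gap either. That the question is put only once is also an inference, from its absence in the listed contacts.

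A reader might take 7 ml/kg over 8 weeks as the one limit the protocol adopts. It is one of two routine limits cited, and the limit expressly applied to the clamp is the single-draw one. Still, the appeal to three-month spacing makes sense only for a cumulative limit, so the 8-week guideline is in use implicitly.

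A reader might also take the co-enrollment sentence in section 8 (Subject Compensation) as evidence of doubled clamps. It says the reverse: the other study performs Visits 4 and 8 in place of this one. It shows only that concurrent participation is foreseen.

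Finally, every illustrated breach needs an assumed outside volume and a weight at which the clamp alone already exceeds 3 ml/kg. Hemoglobin is rechecked at Visit 5, a value below 9 leads to withdrawal, and section 10 allows the stored sample to be left out. These points limit the size of the problem; they do not remove the mismatch of periods.

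**Conclusion.** The point holds as a minor inconsistency in a safety check. The question's period does not match the cumulative guideline's period, and no repeat before either clamp is described. The uncovered time, at least 14 of 56 days before the first clamp and 56 of 56 before the second, is a property of the question alone. It rests on consent at Visit 1, clamps 84 to 91 days apart, and no unrecorded repeat. The joint coverage of question and tracking system cannot be computed from the documents.

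The stronger conclusion, that participants will exceed 7 ml/kg, is not supported. It would need a light participant, a second blood-drawing study of sufficient volume, and a miss by the tracking system. The practical effect is small.

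**What to change.** Reconcile sections 9 and 10 so that the look-back and the cumulative guideline use the same period; the choice of period is the sponsor's. State what the tracking system covers, over what period, and when it is consulted. Recheck participation in other studies, by question and by tracking system, at an existing contact before Visit 4 and again before Visit 8, and compare any reported volume plus this trial's draws with the guideline. The recheck matters more than the length of the consent look-back, since only the recheck reaches the second clamp.

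The cost is a short text change and two brief questions at contacts that already take place. The conflict between 130.8 ml, 26 kg and 3 ml/kg is not resolved by this change and must be reconciled on its own.

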#### 4. Study Visits

**Table 2: Study Timeline**

|   | V 1
Screen | BASELINE ASSESSMENTS |           |               | TREATMENT ASSESSMENTS |             |            |                   |
|---|---------------|----------------------|-----------|---------------|-----------------------|-------------|------------|-------------------|
|   |               | V2
MRS 1          | V3
CV1 | V4
Clamp 1 | V5
PC              | V6
MRS 2 | V7
CV 2 | V8*
Clamp
2 |
| Serum Cr, AST, ALT
History & Physical                | X             |                      |           |               | X                     |             |            |                   |
| Hemoglobin  | X             |                      |           |               | X                     |             |            |                   |
| Accelerometer   | X             |                      |           |               |                       |             |            |                   |
| Height, Weight  | X             | X                    | X         | X             | X                     | X           | X          | X                 |
| Waist Circumference                                     | X             |                      |           | X             | X                     |             |            | X                 |
| BP  | X             |                      | X         | X             | X                     |             | X          | X                 |
| HbA1c, Insulin Dose                                     | X             |                      |           | X             | X                     |             |            | X                 |
| Pregnancy Test  |               |                      |           | X             |                       |             |            | X                 |
| DEXA Scan   |               |                      |           | X             |                       |             |            | X                 |
| Insulin Clamp   |               |                      |           | X             |                       |             |            | X                 |
| Urine MMPs  |               |                      |           | X             |                       |             |            | X                 |

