## **B. Serious Adverse Events (SAE)**

### **1. Serious Adverse Event Definition**

Events are divided into those that are not serious (AE) and those that are serious (SAE). The distinction between an SAE and an AE is a regulatory definition established by the FDA, not a clinical definition. The definition of SAE is not always related to clinical severity of the event. For the purposes of this study an AE is considered a Serious (SAE) when it satisfies any one of the following criteria:

- The event results in an inpatient hospitalization (any overnight stay associated with an admission).
- The event results in the prolongation of a hospital stay.
- The event results in permanent or severe disability.
- The event results in death.
- A pregnancy results in a congenital anomaly.
- The event results from an overdose (either accidental or experimental) of the study medication.
- The event is life-threatening.
- Treatment is required to prevent a serious event.
- The patient experiences a bout of lactic acidosis.
- An episode of severe hypoglycemia requiring assistance occurs.

There have been no SAE's in the research groups experience in the Pediatric CTRC. We do not anticipate encountering SAE's; however, we have identified the following as possible SAE's for the purposes of monitoring:

- Infection related to blood draw or IV placement
- Severe hypoglycemia during the euglycemic clamp or VO2 max test (blood glucose < 45 mg/dl)
- Severe adverse effects from taking placebo or metformin

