### **a) Serious Adverse Event Reporting**

Study patients are instructed to contact the clinic with any serious adverse event meeting the above criteria. Each SAE is recorded on the study form and the PI is informed soon as possible after they occur and preferably within 24 hours of the notification of the clinic staff. This notification should occur even if data are incomplete. Additional data and follow-up information are documented and sent subsequently as an update to the original report. The PI immediately forwards SAE reports to the Safety Officer and COMIRB and any other required institutional monitoring committee.

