## **C. Subject Discontinuation Criteria**

If a subject experiences any of the following, the subject will be withdrawn from the study.

1. Inability to complete study procedures
2. Inability of subjects to tolerate a minimum of 500 mg BID of metformin or placebo tablets
3. Development of anemia or renal dysfunction (anemia: hemoglobin < 9; renal dysfunction: creatinine >1.2)
4. Recurrent severe hypoglycemia (severe defined as symptomatic blood glucose < 45 mg/dl requiring assistance or seizure; recurrent as determined by PI)
5. Development of Lactic acidosis (as determined by PI)
6. Subject becomes pregnant during study

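### Pregnancy on study requires withdrawal, yet no pregnancy test falls during the roughly 90-98 days on blinded drug; a urine test at Visit 5 would cut the longest untested interval to about 45-58 days (minor).

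*Combined protocol and SAP*

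**What the plan says.** Section VIII.C, Subject Discontinuation Criteria, lists "Subject becomes pregnant during study" among the events that lead to withdrawal. In Table 2 the row "Pregnancy Test" is marked at Visits 4 and 8 only. Section V.10, Protection Against Risks, explains the purpose: "Women will have a urine pregnancy test performed in order to ensure that neither the DEXA nor the clamp study is performed" in a pregnant woman. It adds: "Pregnancy is an exclusion criterion in the study and is tested for prior to each DEXA and insulin clamp". The Visit 4 text says that a participant found pregnant is withdrawn and referred to her diabetes physician, and Visit 8 repeats the Visit 4 procedures.

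Drug begins with dinner after the Visit 4 clamp (Visit 4) and is taken until Visit 8 is complete (Phone Interview 2). Six weeks of supply are dispensed at Visit 4 and eight more at Visit 5, which falls 45 days (+/- 5) after Visit 4. Visit 5 covers adverse events, medical history changes, HbA1c, liver enzymes, creatinine and hemoglobin. Table 2 also marks "History & Physical" there. Neither the table nor the Visit 5 text includes a pregnancy test.

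On outcomes, the SAE definition includes this criterion: "A pregnancy results in a congenital anomaly". Pregnancy itself is not on that list.

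**The concern.** One test precedes the first dose and the other comes at the last treatment visit. The withdrawal rule is therefore never checked by a test while the participant is taking drug. A participant with an unrecognised pregnancy would stay on blinded metformin or placebo until Visit 8, although the protocol wants her withdrawn, and Visit 5 would hand her the second supply. Visit 5 is the natural place for a check: it is in person, it falls near the middle of treatment, and it already repeats the laboratory values behind another withdrawal criterion (hemoglobin below 9, creatinine above 1.2) at the visit where drug is re-dispensed.

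What is at stake is the length of exposure in a rare case. No efficacy estimate is involved.

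**Working it through.** The plan gives no figure for the untested interval, so there is none to reproduce. The check is calendar arithmetic.

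**Inputs from the protocol**
- Planned treatment: 3 months, taken as 90 days. No day window is given for Visit 8.
- Supply: 6 weeks + 8 weeks = 42 + 56 = 98 days, used as the upper value for the day of Visit 8.
- Visit 5: day 40 to 50.
- Participants: 60 completers (Enrollment) or 80 randomized (Data Analysis Plan). About half are expected to be female (Inclusion of Women), so 30 to 40.

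**Interval now.** With T the day of Visit 8, the untested interval on drug is T, which is 90 to 98 days.

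**Interval with a test at Visit 5 on day v.** The longest gap is max(v, T - v).

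| T | v = 40 | v = 45 | v = 50 |
|---|---|---|---|
| 90 | 50 | 45 | 50 |
| 98 | 58 | 53 | 50 |

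The range is 45 to 58 days. If Visit 5 falls on day 50 and the full 8 weeks are counted from then, Visit 8 could be as late as day 106. The present gap would then be 106 days, and the gap with a Visit 5 test 56 days, still within the range.

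**Drug days spared.** T - v runs from 90 - 50 = 40 to 98 - 40 = 58. This is a maximum, because it assumes that nobody would have recognised the pregnancy before Visit 8.

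**Expected numbers.** The documents give no pregnancy rate. I assume 1% to 5% per year.
- Person-years over 90 days: 30 x 90/365.25 = 7.39; 40 x 90/365.25 = 9.86.
- On-drug pregnancies, both arms: 7.39 x 0.01 = 0.07 to 9.86 x 0.05 = 0.49. About half would be on metformin: 0.04 to 0.25.
- Share that a day-45 test could find: 45/(90 + L), where L is the assumed lag from conception to a positive test. L = 0 gives 50%, L = 14 gives 43%, L = 21 gives 41%.
- Number findable at Visit 5: 30 x 45/365.25 x 0.01 = 0.04 to 40 x 45/365.25 x 0.05 = 0.25. About half would be on metformin: 0.02 to 0.12.

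The upper values give every female participant a full treatment period and ignore the 30% dropout that the protocol allows for.

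**The case against.** The strongest reply is that the protocol has reasons for light monitoring. The Metformin Intervention section notes that the drug is commonly continued through the first trimester and presents the pregnancy exclusion as an added precaution. The phone calls and Visit 5 ask about adverse events and medical history. Booking Visit 8 for the early follicular phase where possible may prompt a menstrual enquiry. Expected cases are far below one. All of this stands and keeps the severity minor. It does not supply a check for a pregnancy that the participant has not recognised, which is the case a test is for.

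A reader might go on to infer three stronger points that the documents do not support.
- *That on-drug pregnancies have no route to outcome reporting.* Serious Adverse Event Reporting tells participants to contact the clinic about any listed SAE, which includes a congenital anomaly. It also provides for follow-up updates, and "The PI immediately forwards SAE reports to the Safety Officer and COMIRB and any other required institutional monitoring committee". The diabetes physician to whom a participant is referred may be at the investigators' own centre (Subject Recruitment Plan). An undated call to families after the study is planned as well (Exercise Prescription). Only active study follow-up is absent from the supplied text, and the consent pages, which may cover pregnancy reporting or contraception, were not available.
- *That the protocol is inconsistent because its other withdrawal criteria are all tested.* They are not. Lactic acidosis and recurrent severe hypoglycemia are left to the PI's determination, and no lactate test is scheduled.
- *That participants face a known fetal hazard.* The protocol makes no such statement and leans the other way.

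**Conclusion.** The point holds as a minor safety-monitoring improvement. The protocol requires withdrawal for pregnancy, but schedules no test between the pre-dose visit and the end of treatment. A Visit 5 urine test would reduce the longest untested interval from about 90-98 days to about 45-58 days. That shortens the gap without closing it. The benefit is up to 40-58 fewer days of drug for a participant whose pregnancy would otherwise be missed until Visit 8, and such cases are expected to number well under one.

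The interval figures rest on taking 3 months as 90 days and on the dispensed supply as the upper limit. The case counts rest on the assumed rate of 1% to 5% per year. Follow-up of a pregnancy to outcome is an optional clarification and not a gap of the same standing.

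**What to change.** In Table 2 and the Visit 5 text, add a urine pregnancy test for female participants, done before the second 8-week supply is dispensed. If it is positive, stop study drug and withdraw the participant under the existing discontinuation criterion.

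Optionally, add a sentence to Subject Discontinuation Criteria: a pregnancy on study drug is reported to the Safety Officer and, with the participant's consent, followed by phone until the outcome is known.

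The cost is an amendment with any needed consent wording and about 40 dip tests, of a kind already used at Visits 4 and 8, at a visit that already takes place. The optional sentence would add a few calls in rare cases. A participant who tests positive would give no Visit 6 or Visit 7 data, so her follow-up ADP half-time, BrachD and circumferential strain would be lost. If she were still pregnant at Visit 8, her clamp and DEXA would be cancelled under the present plan anyway.
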